4.5. Study sample size

The inclusion of a total of 250 patients with genitourinary tumors presenting with COVID-19 infection is expected, sufficient to respond to the objectives set by the study.

Given the characteristics of the study, the total number of patients cannot be previously calculated accurately, although the inclusion of approximately 250 patients is expected. The planned analysis is the descriptive one of each of the variables. The qualitative variables will be compared with each other using the Chi-square test. Quantitative and qualitative analysis using Student's T analysis or ANOVA. If necessary, the corresponding non-parametric tests will be applied. Survival will be calculated using Kaplan-Meyer curves and curve comparison using Log-Rank.

The Statistical Package for the Social Sciences (SPSS) will be used for statistical analyses. Additional analyzes could be performed with other statistical analysis packages.

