2.2.3. Data reported in the oncology population

Although so far there is no evidence of the behavior of SARS-CoV-2 in the oncology population, it is possible that patients undergoing immunosuppressive oncology treatment may have a greater susceptibility to it and a higher incidence of associated complications than the general population, such as and as occurs with other respiratory viral infections such as the flu.

There is no evidence that the virus worsens the tumor pathology itself and in many cases it has a mild clinical course. However, in cancer patients it could be associated with a more severe clinical picture, the severity of which could be increased if other factors such as advanced age or the presence of other comorbidities are associated. This increased risk of complications requires strict compliance with prevention protocols and extreme caution. The recommendations made to avoid contagion to the general population must be followed particularly strictly by cancer patients.

Several overview reviews have been published (especially of Chinese and Italian experiences). The most commented article, published in Lancet Oncology a few weeks ago, reveals the possibility that cancer patients have a worse prognosis when suffering from COVID-19⁽¹⁾, but it is also true that this cohort of patients had a higher median age than for those without cancer and the proportion of patients is so small that there may be great heterogeneity in that population (cured vs. metastatic patients, etc.). To this we must add that the risk for cancer patients is also related to a greater inability to receive necessary medical care.

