Despite this, recently, a new retrospective review has been published in Annals of Oncology with 28 COVID-19 + oncology patients.⁽²⁰⁾ The most common tumor in this series was lung cancer (25%), with only 3 patients with genitourinary cancer (2 patients with prostate cancer and 1 patient with testicular cancer). The median age was 65 years. The most common symptoms were fever (82.1%) and cough (78.6%), and the most common laboratory abnormalities were lymphopenia (82.1%) and elevated CRP (82.1%). The risk of severe complications was higher in patients who had received oncological treatment in the 14 days prior to the diagnosis of the infection, with an HR in the multivariate analysis adjusted for age and sex of 4.079 (95% CI 1.086-15.322, p 0.037). However, despite being the largest series collected of COVID-19+ oncology patients, it has its limitations, which are mentioned in the article itself. To begin with, this is a retrospective study of 28 patients. Furthermore, the population is heterogeneous, with different tumors and stages (64.3% are stages I-III), which is not taken into account in multivariate analysis. A more recent article in Cancer Discovery with 69 patients with lung cancer, mainly active or metastatic (80%), determined that previous oncological treatment with Programmed Dead-1 (PD-1) blockers does not have a significant impact on severity of COVID-19 infection⁽²¹⁾.

23. Working hypothesis

The identification of patients with genitourinary tumors who suffer from infection with the SARS-CoV-2 agent can represent multiple benefits both for themselves and for health professionals and the health system itself. We would be able to know more precisely the clinical evolution of this type of patient, know their prognosis and be able to select the most appropriate treatment modality for future pandemics.

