4. STUDY METHODOLOGY

4.1. Study type and design

This is a national multicenter, observational, retrospective and prospective post-licensure (EPA-AS) study that will include patients with genitourinary tumors presenting with COVID-19 infection.

The study will be carried out in Spanish hospital centers, with principal investigators belonging to the medical oncology services of the SOGUG group (Spanish Genitourinary Oncology Group), who will act as sponsor. Once the patients are selected, the variables described in section 5 of this protocol will be collected and studied.

The study will use data obtained from the patient's medical history, with no plans to use other sources.

The assignment of a patient to a specific therapeutic strategy has already been decided in advance by the usual clinical practice of medicine; The decision to prescribe a specific treatment is clearly dissociated from the decision to include a patient in the study. No intervention, whether diagnostic or follow-up, will be applied to patients other than standard clinical practice. Epidemiological methods will be used to analyze the data collected.

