6. PROTECTION OF HUMAN SUBJECTS

6.1. Applicable legislation

This is an observational, descriptive, non-interventional study with the main objective of collecting information on patients with genitourinary tumors who present COVID-19 infection, under clinical care and follow-up in the departments of participating centers distributed nationwide.

The study design includes the collection of retrospective and prospective data, promoted by the Spanish Genitourinary Tumors Group (SOGUG) and is considered of public interest. Therefore, in accordance with Order 3470/2009 of Health and Social Affairs (SAS), of December 16, the Sponsor has requested the EPA-AS classification from the AEMPS. This classification has been ratified by the AEMPS on April 23, 2020. In accordance with the same legislation, the participation of any center will be subject to the approval of the Post-authorization Studies Coordination Committee, a favorable opinion from a Clinical Research Ethics Committee accredited in Spain and the approval of the management of each participating center.

Participating in this study does not represent any additional risk for patients because it is a study developed from information recovered from the clinical history and clinical evaluation of patients, all in the context of usual clinical practice and without participation of the patients. patients in any type of intervention or without the modification of the treatment that they would receive if they had not participated in the study.

This protocol will be carried out in accordance with the principles adopted by the 18th World Medical Assembly (Helsinki, 1964) and its subsequent amendments (Fortaleza, 2013), following the rules of good clinical practice and the code of ethics.

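### Section 4.5 names only unadjusted tests, although three main objectives relate cancer treatments chosen in routine care to the course of COVID-19

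*Combined protocol and SAP*

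**What the plan says.** The statistical plan is one paragraph in section 4.5. It opens with "The planned analysis is the descriptive one of each of the variables". For comparisons it adds "The qualitative variables will be compared with each other using the Chi-square test", then Student's t-test or ANOVA with non-parametric alternatives, and "Survival will be calculated using Kaplan-Meyer curves and curve comparison using Log-Rank". It names no regression model, stratified test, matching, propensity method or covariate list, and neither does any other section supplied. The nearest wording elsewhere is in section 4.1: "Epidemiological methods will be used to analyze the data collected".

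The main objectives (section 3.1, numbered i to v in the summary, section 1.2) go beyond description. Objective ii asks about a possible relationship between cancer treatments and the evolution of the infection. Objectives iii and v use the word *impact*, for immunotherapy and for ADT/NAH with or without corticosteroids. Section 4.1 says of treatment: "The assignment of a patient to a specific therapeutic strategy has already been decided in advance by the usual clinical practice of medicine".

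**The concern.** Patients given immunotherapy, chemotherapy, ADT or follow-up only are likely to differ in age, stage, comorbidity and tumour type. The protocol recognises the problem. Section 2.2.3 says of the clinical picture in cancer patients: "the severity of which could be increased if other factors such as advanced age or the presence of other comorbidities are associated". Among the limitations of a cited 28-patient series, which did adjust for age and sex, it reports that "the population is heterogeneous, with different tumors and stages (64.3% are stages I-III), which is not taken into account in multivariate analysis".

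A chi-square or log-rank test of treated against untreated patients cannot separate the treatment from the kind of patient who receives it. A crude difference could be read as harm or benefit of a treatment, or a real association could be hidden. A larger sample does not shrink this bias. Tumour type is not a confounder within objective v, which is confined to prostate cancer; age, stage and comorbidity still are.

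**Working it through.** **The plan's own figure.** The only figure is the approximate 250 patients. It comes without alpha, power, effect size, event rate or group sizes, so it can be neither reproduced nor refuted.

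**Step 1. Can a crude test mislead at this size?** All inputs here are assumptions: one confounder (older age), no treatment effect within age groups, and a two-sided 5% test.

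Crude mortality p = (share older × mortality in older) + (share younger × mortality in younger).

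Rejection rate = Φ((d − c)/s₁) + Φ((−d − c)/s₁), where d = p₁ − p₂, c = 1.96·√[p̄(1−p̄)(1/n₁+1/n₂)] and s₁ = √[p₁(1−p₁)/n₁ + p₂(1−p₂)/n₂].

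Central case: p₁ = 0.60×0.35 + 0.40×0.10 = 0.250 and p₂ = 0.25×0.35 + 0.75×0.10 = 0.1625. OR = (0.250/0.750)/(0.1625/0.8375) = 1.72. At 125:125, d = 0.0875, c = 0.1003 and s₁ = 0.0509, so the rejection rate is 0.40.

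| | Mild | Central | Strong |
|---|---|---|---|
| Share older, treated v untreated | 50% v 30% | 60% v 25% | 70% v 20% |
| Mortality, older / younger | 30% / 15% | 35% / 10% | 35% / 10% |
| Crude mortality | 22.5% v 19.5% | 25.0% v 16.25% | 27.5% v 15.0% |
| Crude OR (true OR 1) | 1.20 | 1.72 | 2.15 |
| Crude OR if treated are the younger group | 0.83 | 0.58 | 0.47 |
| Rejection, 125:125 | 9% | 40% | 68% |
| Rejection, 50 treated : 200 | 8% | 32% | 54% |
| Rejection, 50:50 | 7% | 19% | 33% |
| Rejection, 40:40 | 6% | 16% | 27% |

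Masking: double the odds of death in both age groups and make the treated the younger group. In the central case, 35% becomes 51.9% and 10% becomes 18.2%. Treated mortality is then 0.25×0.519 + 0.75×0.182 = 0.266 against 0.250, a crude OR of 1.09. The mild and strong cases give 1.63 and 0.87.

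**Step 2. How much adjustment can the study carry?** Assume one model term per 10 events, or per 10 non-events if these are fewer.

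- Deaths, whole cohort: under the step 1 assumptions 44 to 63 are expected. The lowest is 50×0.275 + 200×0.15 = 43.75; the highest, with the treated younger, is 50×0.15 + 200×0.275 = 62.5. That allows 4 to 6 terms.
- Deaths, an assumed prostate subgroup of 80 to 100: about 17 to 21, or 1 to 2 terms.
- Admission, if 40% to 60% are admitted (assumed): at least 100/10 = 10 terms in 250 patients, 4 to 5 in 100 and 3 to 4 in 80.

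**Step 3. Spend the terms.** Section 5.1 lists six treatment types: surgery, radiotherapy, chemotherapy, immunotherapy, targeted drugs and hormone therapy. Coded together they use five terms, leaving at most one covariate out of 4 to 6 in a death model.

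A single contrast is affordable. Immunotherapy yes/no (1), age (1), a comorbidity count (1) and two-level stage (1) make 4 terms. Adding the four tumour groups of section 4.3 (3 terms) makes 7, which fits the admission model but not the death model.

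For objective v, three ADT/NAH categories use 2 terms. That leaves 1 to 3 covariates for admission and none for death.

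**The case against.** The strongest reply is that the study claims no more than description: "This is an observational, descriptive, non-interventional study", and section 4.5 says the same of its analysis. Objective ii asks only for a possible relationship. This reply holds for mortality, admission and asymptomatic rates, where crude percentages are what is wanted. It does not hold for objectives iii and v, which ask for impact, or for a plan that names between-group tests.

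A reader might infer that the protocol rules adjustment out. The documents do not support that. The open wording in section 4.1, and the sentence in 4.5 allowing additional analyses in other packages, neither name nor exclude it. The gap is that nothing is specified.

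A reader might also take the 6% to 68% as this study's error rate. It is not: every input is assumed, and the mild case is close to nominal. Nor should the remarks on the 28-patient series be read as purely the protocol's own criticism, since section 2.2.3 introduces its limitations as ones mentioned in the article itself.

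The most practical objection is that events are few and treatments follow tumour type, so much of objective ii may not be adjustable. That stands, and it shapes the fix. Admission is also an imperfect outcome, because the threshold for admitting a patient may depend on cancer treatment. Survival to consent and the dating of serology-only cases are separate questions and form no part of this point.

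**Conclusion.** The point holds for objective ii, objective v and the part of objective iii on how immunotherapy affects the infection. Followed as written, section 4.5 gives only crude comparisons of groups formed by clinical choice. The documents establish the omission. They do not establish the size or direction of any bias; the calculation shows only that, at about 250 patients, confounding could plausibly create or hide an association. The tempting stronger conclusion, that the treatment results will be wrong or that one adjusted model would make them right, is not supported. No performance status or frailty measure is listed in section 5.1, so adjustment would reduce confounding and leave some behind. This is a cheap improvement, and the descriptive aims stand as they are.

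**What to change.** In section 4.5:

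- For treatment received before or at infection, make the main comparison a short prespecified logistic model, with crude results alongside. Fit it for hospital/ICU admission, and for death where events allow.
- Use covariates already in section 5.1: age, a single comorbidity term (for example a count), stage at infection, and tumour type where treatment groups overlap.
- Use few treatment contrasts per model, for example immunotherapy yes/no, and ADT/NAH categories within prostate cancer.
- Fix the covariates and the number of terms from the total event count before looking at treatment effects.
- Label as unadjusted and hypothesis-generating: any comparison that cannot carry a covariate (likely many-category comparisons of death, and objective iv), treatment given after infection, and the effect of COVID-19 on immunotherapy toxicity, for which there is no uninfected comparator.
- State that residual confounding remains, that the admission threshold may itself depend on cancer treatment, and that associations are not causal.

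The cost is a paragraph of text and modest analysis time, with no new variables. The downsides are wider intervals, few covariates, and limited overlap of treatments across tumour types.

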3. OBJECTIVES

3.1. Main objectives

- Describe the population infected by COVID-19 with genitourinary tumors (urothelial cancer, prostate cancer, testicular cancer and renal cancer) treated in Spanish hospitals, know the clinical presentation, therapeutic evolution and prognosis of said intercurrent infectious process, as well as its possible relationship with different clinical and therapeutic factors.
- Assess the possible relationship of the different oncological treatments administered to these patients with the clinical evolution of COVID-19 infection, considering both patients who have undergone oncological treatment previously, during or after COVID-19 infection.
- To specifically evaluate the impact of COVID-19 infection on the toxicity of immunotherapy treatment (mainly pneumonitis) and the impact of immunotherapy on the evolution of the infectious condition in patients with tumors of genitourinary origin, in three different scenarios: during treatment, after treatment and in patients who are prescribed treatment after the infection has passed.
- Analysis of this same relationship in patients with genitourinary tumors and asymptomatic COVID-19 infection with positive Ab serologies (IgM and IgG).
- To evaluate in patients with Prostate Cancer (PCa) the impact of androgen deprivation therapy (ADT) and new antiandrogen agents (NAH) with or without corticosteroids on infection COVID-19.

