5. VARIABLES

5.1. Study variables

A data collection notebook will be prepared in which the following variables will be collected for analysis:

Affiliation of the center:

- Hospital name
- Province
- Investigator's name
- Patient number

Patient characteristics:

- Age
- Sex
- Age
- Hospital center where the patient is recruited (in order to have epidemiological data on the pandemic that may be of interest)

Pathological history:

- Concomitant pathology (cardiac, pulmonary, renal, liver, Diabetes Mellitus, HIV, AI)
- Usual pharmacological treatment
- Smoking and alcohol habit

Tumor pathology:

- Tumor type, histology and stage (initial and at diagnosis of infection)
- Date of cancer diagnosis
- Active cancer treatment or follow-up
- Participation in clinical trial
- Type of treatment most recently received for the infection (Surgery; Radiotherapy; Chemotherapy: Drug, Immunotherapy, TD: Drug, HT: ADT alone or with Abiraterone, Enzalutamide, others)
- Treatment lines
- Start and last dose received of the most recent oncological treatment

For patients with prostate cancer:

- Local treatment and type (Surgery, Radiotherapy)
- Adjuvant ADT or advanced disease (start date)
- NAH (date and line of treatment)
- Associated corticosteroid treatment: Prednisone vs Dexamethasone (dose)

COVID-19 infection data:

- Confirmation date of COVID-19 infection
- PCR diagnostic test
- IgG or IgM serological diagnostic test
- Present symptoms

- Analytical alterations, lymphopenia, elevated CRP, high D-dimer.
- Thrombosis associated with COVID-19 infection
- Date of onset and disappearance of symptoms
- Days duration of fever and cough
- Radiological examination at the moment of greatest severity
- Complications of infection: presence of complications and/or hospital or ICU admission
- Admission date
- Date of most serious complication
- Treatments received for COVID-19
- Discharge status
- Fecha de alta / exit
- Negativization of the presence of viruses by PCR
- Negative PCR date

For patients who are receiving or have received immunotherapy treatments, additional information will be collected:

- Immunotherapy treatment line
- Start/end date of immunotherapy treatment
- Date of last dose received prior to COVID-19 infection
- Immunotherapy received as monotherapy or combination
- Type of immunotherapy
- Adverse effects

Prospective follow-up data (6 months from patient inclusion):

- Date of start or restart of oncological treatment after infection

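### Section 4.5 addresses the treatment–COVID-19 objectives with tests alone: no effect estimate, interval, significance level, key contrast or exploratory label

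*Combined protocol and SAP*

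**What the plan says.** The analysis plan of the combined protocol and SAP is contained in section 4.5. It first states "The planned analysis is the descriptive one of each of the variables". It then names tests: "The qualitative variables will be compared with each other using the Chi-square test"; "Quantitative and qualitative analysis using Student's T analysis or ANOVA"; non-parametric alternatives where needed; and "Survival will be calculated using Kaplan-Meyer curves and curve comparison using Log-Rank". It lists no comparisons. It gives no significance level, primary outcome, primary contrast, effect measure, confidence interval or approach to multiplicity, and does not say that results are exploratory. The only confidence intervals in the document belong to cited studies (sections 2.2.2 and 2.2.3).

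Section 3.1 sets five unranked main objectives. The first is partly descriptive but extends to the infection's course "as well as its possible relationship with different clinical and therapeutic factors". Others ask about the relationship of oncological treatments with the clinical course, the impact of immunotherapy, and the impact of androgen deprivation and newer antiandrogens in prostate cancer.

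Section 3.2 does give concrete measures of the course: death at discharge, complications needing hospital or ICU admission, and asymptomatic or mild infection. It presents them as percentages, not contrasts. Section 6.1 again describes the study as observational and descriptive.

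**The concern.** Relationship and impact are comparative questions, and section 4.5 answers them with hypothesis tests and nothing else. Two errors become possible.

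First, the clinical course is not defined for objectives ii to v. Section 5.1 offers symptoms, laboratory changes, thrombosis, radiology, complications, admission and discharge status. Treatment can be split by type, line, timing, or active therapy versus follow-up. With no pair named in advance, a small p-value can be picked out afterwards, and the reader cannot tell how many pairs were examined.

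Second, a chi-square test without an estimate says nothing about precision. In a small treatment subgroup, a non-significant result may be taken as evidence that the treatment does not matter when the data are compatible with a large difference either way.

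This matters because the working hypothesis at the end of section 2 hopes that the findings will inform the choice of treatment in later pandemics.

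**Working it through.** **The plan's own figure.** The only design figure is the sample size: "the inclusion of approximately 250 patients is expected". It cannot be reproduced or refuted, because no level, power, event rate or effect size is given and the plan itself says "the total number of patients cannot be previously calculated accurately".

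**Inputs.**
- Variables: section 5.1 ("A data collection notebook will be prepared in which the following variables will be collected for analysis"). My count, not a protocol figure, is 32 qualitative items at bullet level, leaving out centre and identifiers: 1 patient characteristic + 3 history + 5 tumour + 4 prostate + 10 COVID-19 + 4 immunotherapy + 5 follow-up = 32. Splitting compound bullets (seven comorbidities, three laboratory alterations, hospital and ICU admission, and so on) gives about 46.
- Significance level: not stated; 0.05 two-sided per test is assumed.
- Grid sizes for treatment by course: assumed, since the plan fixes none. I use 4×4, 5×5 and 10×9.

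**Literal reading, every qualitative pair.** Pairs = k(k−1)/2; expected false positives = 0.05 × pairs if nothing is related.
- k = 32: 32×31/2 = 496 pairs; 0.05×496 = 24.8.
- k = 46: 46×45/2 = 1035 pairs; 0.05×1035 = 51.75.

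Many of these pairs (smoking by histology, for example) have nothing to do with treatment and COVID-19. Others, such as complications and discharge status, are surely related. The expected counts are therefore upper-end illustrations.

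**Treatment by course only.** For m independent tests, the chance of at least one false positive is 1 − 0.95^m. Treatment items are correlated with each other, and so are outcomes. I therefore also simulated 2×2 chi-square tests with n = 250, assumed prevalences of 30% (treatment) and 25% (outcome), no true association, and latent correlation 0.7 within each block.

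| Grid | Tests m | Expected false positives (0.05×m) | At least one, independent | At least one, correlation 0.7 |
|---|---|---|---|---|
| 4×4 | 16 | 0.8 | 56% | 44% |
| 5×5 | 25 | 1.25 | 72% | 56% |
| 10×9 | 90 | 4.5 | 99% | 89% |

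Correlation lowers the chance of at least one false positive but not the expected number. To reach 95%, ln(0.05)/ln(0.95) = 58.4, so 59 independent tests are needed.

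**What a test without an interval hides.** Assume 40 treated and 210 untreated patients, with a 25% event rate in both. The 95% half-width for the risk difference is 1.96 × √[0.25×0.75×(1/40 + 1/210)] = 1.96 × 0.0747 = 0.146, about ±15 percentage points. For comparison, one proportion near 50% in all 250 patients has half-width 1.96 × √(0.25/250) = 0.062. The sample describes the whole cohort fairly well and small treatment contrasts poorly, and a bare p-value does not show the difference.

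**The case against.** The strongest reply is that the study is descriptive. Section 4.5 says so immediately before the chi-square sentence, section 6.1 repeats it, and nothing claims to be confirmatory. Formal control of the familywise error rate is not obligatory in such a study, so its absence is not in itself a fault. That stands.

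A reader might infer from the chi-square sentence that the protocol commits to testing every pair, so that hundreds of tests will be run and chance findings on treatment and COVID-19 course are near certain. The documents do not support this. The sentence sits in a list that matches a method to each variable type, and can simply mean that chi-square is used when two qualitative variables are compared. The 5% level is not in the text, nor is any commitment to report p-values. Near certainty on treatment and course also needs roughly 59 or more nearly independent tests.

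Nor are the key comparisons blind picks: section 2.1 gives a rationale for immunotherapy and pneumonitis and for corticosteroids in prostate cancer, and section 3.1 names these exposures.

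The descriptive label does not, however, answer the rest. Section 3.1 asks relational questions and section 4.5 offers tests for them. A descriptive study is better served by estimates with intervals, and the plan provides for none.

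**Conclusion.** The concern holds in limited form. The relational main objectives are addressed by tests alone, with no level, key contrast, effect estimate, interval or exploratory label. The chance of at least one false positive on treatment and course is about 44% to 99%. That range rests on an assumed level of 0.05, no true association, grids of 16 to 90 tests, and correlation from none to 0.7. Even the low end is nearly nine times the nominal 5%. The figure of about 500 tests applies only to the literal reading and to my count of the variables. Several items apply only to prostate or immunotherapy patients, so sparse cells could move the true chi-square error rate away from 5%.

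It would go too far to conclude that the study must control familywise error. The firmer conclusion concerns reporting: without estimates and intervals, neither a significant nor a non-significant result for treatment can be interpreted properly.

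**What to change.** Replace the chi-square sentence in section 4.5 with wording to this effect: associations of treatment or baseline factors with death at discharge, hospital or ICU admission, and asymptomatic or mild infection will be reported as risk differences or odds ratios with 95% confidence intervals; they are exploratory and not adjusted for multiplicity; any p-values shown are descriptive. These outcomes are already in section 3.2, so no new data are needed. For objective iv, which is restricted to asymptomatic infection, the third outcome does not vary and should be left out.

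Naming one contrast for each of objectives ii to v and testing the four with Holm's adjustment is possible but not required. Objective iii has two directions and three scenarios, so one contrast would not represent it, and formal testing could lend confirmatory weight to confounded comparisons. Reporting estimates does not remove that confounding either.

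The cost is wording, slightly more tabulation, and fewer results that can be presented as significant.

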4.6. Sampling and recruitment method

Patients will be included consecutively, in accordance with the inclusion/exclusion criteria previously established in sections 4.3 and 4.4 of this protocol. Inclusion will be carried out competitively without restrictions regarding the number of patients included in each center.

In accordance with the definition of the study population and disease established in this scientific report, patients will be selected from the diagnosed/treated cases of genitourinary tumors presenting with COVID-19 infection treated in the Spanish hospital centers participating in the study.

To prevent two or more doctors participating in the trial from registering the same case, a coordinator is designated, who controls the cases included in his center, in hospital centers with several participating doctors, and preventive measures are implemented in the tool that controls duplications. in the variables (such as age, sex, center or diagnosis).

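### Section 4.5 names only pooled-variance tests (Student's t, ANOVA) for quantitative comparisons; if group sizes and SDs both differ, the error rate leaves its nominal level, and Welch's versions would largely prevent this

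*Combined protocol and SAP*

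**What the plan says.** Section 4.5 holds the whole analysis plan in one paragraph. It opens with "The planned analysis is the descriptive one of each of the variables" and then adds group comparisons: chi-square for qualitative variables, Kaplan-Meier and log-rank for survival, and for quantitative variables, with a fallback, "Quantitative and qualitative analysis using Student's T analysis or ANOVA. If necessary, the corresponding non-parametric tests will be applied". What makes the fallback necessary is not said. No unequal-variance version, significance level or interval is named.

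On numbers, the section says "the total number of patients cannot be previously calculated accurately", "although the inclusion of approximately 250 patients is expected". No expected size is given for any subgroup, and no SD for any variable.

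The groups that could be compared come from sections 3.1, 3.2 and 4.3: four tumour types, three immunotherapy scenarios, type of oncological treatment, death or survival at discharge, and hospital or ICU admission. Section 4.6 plans consecutive inclusion and sets no quota for any of these. The quantitative variables in section 5.1 include age and the days that fever and cough lasted. Others can be derived from recorded dates, for instance from "Start and last dose received of the most recent oncological treatment".

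**The concern.** Student's t and classical ANOVA estimate one common variance. With equal group sizes this does little harm to the t-test even when the SDs differ. With unequal sizes it matters. The pooled estimate is dominated by the larger group, so if the smaller group is the more variable one, the standard error of the difference is too small and the test rejects too often. If the smaller group is the less variable one, the standard error is too large and real differences are missed.

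Groups defined by tumour type, treatment or outcome, filled by consecutive accrual, would be of equal size only by chance. Equal spread of durations and ages across such groups cannot be taken for granted either. The p-values and intervals at stake are those that relate quantitative variables to the clinical and therapeutic factors in the main objectives. The rank-test fallback does not settle the matter, because Mann-Whitney read as a test of location also loses its level when spreads differ.

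**Working it through.** **No plan figure to reproduce.** The figure of 250 comes without effect size, SD, power or level, so it cannot be re-derived.

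**Inputs**
- Total of 250 patients: section 4.5.
- Level: not stated; two-sided 5% assumed.
- Group sizes n1 (smaller) and n2 (larger): not stated; a range of splits of 250 assumed.
- SD ratio r = SD of smaller group / SD of larger group: not stated; 0.5 to 2 assumed.
- Distribution: normal with equal means assumed first, then skewed.

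**Formula.** With the larger group's SD set to 1:
- true variance of the difference: V_true = r²/n1 + 1/n2
- variance that Student's t uses, on average: V_pool = [(n1−1)r² + (n2−1)]/(n1+n2−2) × (1/n1 + 1/n2)
- actual error ≈ 2 × [1 − Φ(1.96 × √(V_pool/V_true))]

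**40 v 210, r = 2.** V_true = 4/40 + 1/210 = 0.1048. V_pool = (39×4 + 209)/248 × (1/40 + 1/210) = 1.4718 × 0.02976 = 0.0438. √(0.0438/0.1048) = 0.647; 1.96 × 0.647 = 1.267; error 20.5%.

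**75 v 175, r = 2.** V_true = 4/75 + 1/175 = 0.0590. V_pool = (74×4 + 174)/248 × (1/75 + 1/175) = 1.8952 × 0.01905 = 0.0361. √(0.0361/0.0590) = 0.782; 1.96 × 0.782 = 1.532; error 12.5%.

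**40 v 210, r = 0.5.** V_true = 0.25/40 + 1/210 = 0.0110. V_pool = (39×0.25 + 209)/248 × 0.02976 = 0.8821 × 0.02976 = 0.0263. √(0.0263/0.0110) = 1.544; 1.96 × 1.544 = 3.03; error 0.25%.

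**Simulation** (normal data, 200,000 runs per cell), error rate of Student's t:

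| Split | r = 0.5 | r = 1 | r = 1.5 | r = 2 |
|---|---|---|---|---|
| 15 v 235 | 0.06% | 5.0% | 16.9% | 27.6% |
| 40 v 210 | 0.25% | 5.0% | 13.4% | 20.5% |
| 50 v 200 | 0.4% | 5.0% | 12.0% | 18.0% |
| 75 v 175 | 1.3% | 5.1% | 9.3% | 12.4% |
| 100 v 150 | 2.8% | 5.0% | 7.0% | 8.3% |
| 125 v 125 | 5.0% | 5.0% | 5.0% | 5.1% |

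Welch's t-test lay between 4.9% and 5.2% in every cell.

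**ANOVA.** With four assumed groups of 120/65/50/15 and SDs 1/1/1/2, classical ANOVA rejects about 18% and Welch's ANOVA about 5%.

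**Fallback.** Over r = 0.5 to 2 at 50 v 200, Mann-Whitney rejects between 1.9% and 11%.

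**Power.** At 40 v 210 with r = 0.5, for an effect that Welch detects with 79% power, Student's t has about 40%. With equal SDs, Welch costs about 5 points at 15 v 235 (75.3% against 79.9%) and about 1 point at 40 v 210.

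**Preliminary variance test.** Choosing between Student and Welch by Levene's test does not restore the level in small groups. At 10 v 240 with r = 1.5, Levene's test detects the difference in about 41% of samples and the two-step procedure rejects about 11%.

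**Strong skew.** Here Welch fails too. With equal SDs at 15 v 235 it rejects about 8% (exponential) and 12 to 13% (lognormal, log-scale SD 1), where Student rejects 5%. With r = 2 and lognormal data it rejects about 14% at 15 v 235 and 10% at 40 v 210.

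**The case against.** The strongest reply is that the size of the problem rests on inputs the documents do not contain. There are no group sizes, no SDs and no level, and with equal sizes or equal SDs the t-test is on target. That stands, and the point is therefore conditional.

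The second reply is scope. The study is described as descriptive, and most outcomes are categorical or time-to-event (discharge status, admission, share without symptoms, progression, survival). Those go to chi-square or log-rank. This also stands and lowers the priority. It does not remove the point, because section 4.5 does plan tests on quantitative variables and section 3.1 makes relationships with clinical and therapeutic factors a main objective.

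Third, the name Student's t may be a loose, translated label, and SPSS prints an unequal-variance row anyway. That is possible, but the text then leaves the choice between rows open until the data are seen.

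Fourth, Welch is no cure for skewed durations in small groups. The figures above bear this out, and the remedy is limited accordingly.

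Two supports that might be offered are weak. Section 4.6 says "Inclusion will be carried out competitively without restrictions regarding the number of patients included in each center", but this concerns centres, not tumour, treatment or outcome groups. Time since last dose, compared between patients on treatment and in follow-up, differs almost by definition, so a false-positive rate has little meaning there.

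**Conclusion.** The point holds in conditional form. Section 4.5 names pooled-variance tests only, and nothing in the design keeps the compared groups similar in size. Where sizes and SDs both differ, the tests leave their level in a direction set by which group is the more variable. Splits of 40 v 210 and 75 v 175 with a twofold SD ratio give about 20% and 12%. The reverse ratio at 40 v 210 gives about 0.25% and roughly halves the power. These figures assume a two-sided 5% level, normal data and 250 patients in the comparison.

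A reader might infer that the plan's false-positive rate lies anywhere from near 0 to about 28%. The documents do not support that. The 28% belongs to one assumed case for the t-test (15 v 235, r = 2). It is not a ceiling, since r = 3 gives 42% at the same split, and the ANOVA cases tried reached at most 21%. Nor can one say that the p-values for the main objectives are wrong: that needs sizes and SDs to differ together, and it touches only the quantitative comparisons. Priority is low to moderate.

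**What to change.** In section 4.5, replace the two named tests by wording such as: Welch's t-test or Welch's ANOVA, without a prior test for equal variances, reporting the mean difference with its Welch 95% confidence interval.

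Replace the open-ended fallback by a stated rule: rank tests, or analysis on the log scale, are the method for markedly skewed variables such as durations, especially where a group is small. List those variables in advance. State the significance level. Since rank tests are also sensitive to unequal spread, report medians and quartiles by group beside them, so that a difference in spread is not read as a shift.

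The cost is a few sentences; SPSS, the package named in section 4.5, offers both Welch procedures. The statistical price is about 1 to 5 points of power where variances are equal and one group is small. The remaining risk is Welch's own error rate of about 8 to 14% for strongly skewed data with a group of about 15, which is why the rank or log-scale route must stay in the plan.
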